7.2.4 Final Study Visit

3-month Ambulatory Visit (Visit 2, Day 90 +30 days)

- Record adverse events as reported by participant or observed by investigator.
- Collect all study devices: tablet computer, FitBit, blood pressure cuff monitor
- All study activities to be performed during the final visit have been detailed in Table in Section 7.1.1.
- In order to minimize bias during the GAS assessment, GAS will be conducted by a blinded assessor at this visit.
- Every effort will be made to complete the 3-month visit at or as close to day 90 as possible.

7.2.5 Withdrawal/Early Termination Visit

Participants choosing to withdraw or terminate early from the study will not be required to attend the final study visit. Since they are provided with study-related equipment (tablet computer, or if applicable, FitBit and blood pressure cuff), they will be sent a prepaid box to return this equipment to the study team.

7.2.6 Unscheduled Visit

In the event of an unscheduled visit (hospitalization), the subject will undergo safety screening. Medical records will be evaluated to determine if any study-related adverse events have occurred. All adverse events reported by the subject or observed by the investigator will be documented and reported. Aside from adverse events, information gathered at these unscheduled visits will not be included in the statistical analysis.

8 Assessment of Safety

8.1 Specification of Safety Parameters

Prespecified endpoints related to efficacy and safety are detailed in Section 4.2, Study Endpoints.

8.1.1 Definition of Adverse Events (AE)

An **adverse event** (AE) is any symptom, sign, illness or experience that develops or worsens in severity during the course of the study. Intercurrent illnesses or injuries should be regarded as adverse events. Abnormal results of diagnostic procedures are considered to be adverse events if the abnormality:

- results in study withdrawal
- is associated with a serious adverse event

CONFIDENTIAL

This material is the property of the NYU School of Medicine and Langone Medical Center. Do not disclose or use except as authorized in writing by the study sponsor

- is associated with clinical signs or symptoms
- leads to additional treatment or to further diagnostic tests
- is considered by the investigator to be of clinical significance

8.1.2 Definition of Serious Adverse Events (SAE)

Serious Adverse Event

Adverse events are classified as serious or non-serious. A ***serious adverse event*** is any AE that is:

- fatal
- life-threatening
- requires or prolongs hospital stay
- results in persistent or significant disability or incapacity
- a congenital anomaly or birth defect
- an important medical event

Important medical events are those that may not be immediately life threatening, but are clearly of major clinical significance. They may jeopardize the subject, and may require intervention to prevent one of the other serious outcomes noted above. For example, drug overdose or abuse, a seizure that did not result in in-patient hospitalization, or intensive treatment of bronchospasm in an emergency department would typically be considered important medical events.

All adverse events that do not meet any of the criteria for serious should be regarded as ***non-serious adverse events***.

8.1.3 Definition of Unanticipated Problems (UP)

Unanticipated Problems Involving Risk to Subjects or Others

Any incident, experience, or outcome that meets all of the following criteria:

- Unexpected in nature, severity, or frequency (i.e. not described in study-related documents such as the IRB-approved protocol or consent form, the investigators brochure, etc)
- Related or possibly related to participation in the research (i.e. possibly related means there is a reasonable possibility that the incident experience, or outcome may have been caused by the procedures involved in the research)
- Suggests that the research places subjects or others at greater risk of harm (including physical, psychological, economic, or social harm).

8.2 Classification of an Adverse Event

8.2.1 Severity of Event

For AEs not included in the protocol defined grading system, the following guidelines will be used to describe severity.

- **Mild** – Events require minimal or no treatment and do not interfere with the participant's daily activities.
- **Moderate** – Events result in a low level of inconvenience or concern with the therapeutic measures. Moderate events may cause some interference with functioning.
- **Severe** – Events interrupt a participant's usual daily activity and may require systemic drug therapy or other treatment. Severe events are usually potentially life-threatening or incapacitating.

CONFIDENTIAL

This material is the property of the NYU School of Medicine and Langone Medical Center. Do not disclose or use except as authorized in writing by the study sponsor

8.2.2 Relationship to Study Intervention

For all collected AEs, the clinician on the study team will determine the AE's causality based on temporal relationship and his/her clinical judgment. The degree of certainty about causality will be graded using the categories below.

- **Definitely Related** – There is clear evidence to suggest a causal relationship, and other possible contributing factors can be ruled out. The clinical event, including an abnormal laboratory test result, occurs in a plausible time relationship to drug administration and cannot be explained by concurrent disease or other drugs or chemicals. The response to withdrawal of the drug (dechallenge) should be clinically plausible. The event must be pharmacologically or phenomenologically definitive, with use of a satisfactory rechallenge procedure if necessary.
- **Probably Related** – There is evidence to suggest a causal relationship, and the influence of other factors is unlikely. The clinical event, including an abnormal laboratory test result, occurs within a reasonable time after administration of the drug, is unlikely to be attributed to concurrent disease or other drugs or chemicals, and follows a clinically reasonable response on withdrawal (dechallenge). Rechallenge information is not required to fulfill this definition.
- **Possibly Related** – There is some evidence to suggest a causal relationship (e.g., the event occurred within a reasonable time after administration of the trial medication). However, other factors may have contributed to the event (e.g., the participant's clinical condition, other concomitant events). Although an AE may rate only as "possibly related" soon after discovery, it can be flagged as requiring more information and later be upgraded to "probably related" or "definitely related," as appropriate.
- **Unlikely to be related** – A clinical event, including an abnormal laboratory test result, whose temporal relationship to drug administration makes a causal relationship improbable (e.g., the event did not occur within a reasonable time after administration of the trial medication) and in which other drugs or chemicals or underlying disease provides plausible explanations (e.g., the participant's clinical condition, other concomitant treatments).
- **Not Related** – The AE is completely independent of study drug administration, and/or evidence exists that the event is definitely related to another etiology. There must be an alternative, definitive etiology documented by the clinician.

8.2.3 Expectedness

The Principle Investigators and co-investigators will be responsible for determining whether an AE is expected or unexpected. An AE will be considered unexpected if the nature, severity, or frequency of the event is not consistent with the risk information previously described for the study intervention.

8.3 Time Period and Frequency for Event Assessment and Follow-Up

The occurrence of an AE or SAE may come to the attention of study personnel during study visits and interviews of a study participant presenting for medical care, or upon review by a study monitor. All AEs including local and systemic reactions not meeting the criteria for SAEs will be captured on the appropriate CRF. Information to be collected includes event description, time of onset, clinician's assessment of severity, relationship to study procedures (assessed only by those with the training and authority to make a diagnosis), and time of resolution/stabilization of the event. All AEs occurring during the active 3 month period of the study will be documented appropriately regardless of relationship. All AEs will be followed to adequate resolution.

Any medical condition that is present at the time that the participant is screened will be considered as baseline and not reported as an AE. However, if the study participant's condition deteriorates at any time during the study, it will be recorded as an AE. UPs will be recorded in the data collection system throughout the study.

CONFIDENTIAL

This material is the property of the NYU School of Medicine and Langone Medical Center. Do not disclose or use except as authorized in writing by the study sponsor

Changes in the severity of an AE will be documented to allow an assessment of the duration of the event at each level of severity to be performed. AEs characterized as intermittent require documentation of onset and duration of each episode.

The PI will record all reportable events with start dates occurring any time after informed consent is obtained until the last day of study participation. At each study visit, the investigator will inquire about the occurrence of AE/SAEs since the last visit. Related events will be followed for outcome information until resolution or stabilization.

8.4 Reporting Procedures – Notifying the IRB

8.4.1 Adverse Event Reporting

In the unlikely event that serious and unanticipated and related adverse events or unanticipated problems involving risks to participants or others occur, adverse events will be reported to the NYU SoM IRB, the NIH Program Officer, and the study's DSMB as appropriate (i.e. relationship to study intervention, severity). The Principal Investigators will inform fellow investigators and study personnel, via email, of all adverse events that occur during the conduct of this research project as they are reviewed. The National Institutes of Health will be informed of serious adverse events such as compromise of patient privacy with 7 days of the event becoming known to the principal investigators. Adverse events and serious adverse events occurring during the active period of the study (3 months after baseline visit) will be monitored and reported to DSMB for all study subjects.

8.4.2 Serious Adverse Event Reporting

Serious adverse events will be reported to the NYU SOM IRB, the NIH Program Officer and the study's DSMB as appropriate (i.e. relationship to study intervention, severity). For unanticipated serious adverse events thought to be possibly related to study procedures, the investigator will complete and submit an SAE Form to the NIA Program Officer and to the DSMB Chair or designated DSMB member within 48 hours of study team being notified of the event. A separate report would also be submitted to the NYU SOM IRB in compliance to their Reportable New Information policy as soon as possible, but in all cases within 5 working days. Copies of relevant anonymized medical records will be forwarded to the DSMB as soon as available.

The investigator must complete and submit a follow-up SAE form and additional medical records when additional relevant information becomes available. The investigator will follow all reportable events until resolution or stabilization.

In the event of participant deaths, in compliance with NIA requirements for investigators conducting human intervention studies, all deaths would require expedited reporting (approximately 24 hours after the study team is notified of the death). This report will be submitted to the NIA Program Officer and to the DSMB Chair or designated DSMB member.

Any serious adverse event that is ongoing when a patient completes his/her participation in the trial must be followed by the site investigator until any of the following occurs:

- The event resolves or stabilizes.
- The event returns to baseline condition or value (if a baseline value is available).

All adverse events that do not meet any of the criteria for serious should be regarded as non-serious adverse events.

8.4.3 Unanticipated Problem Reporting

Incidents or events that meet the OHRP criteria for UPs require the creation and completion of an UP report form. The UP report will include the following information:

- Protocol identifying information: protocol title and number, PI's name, and the IRB project number;

CONFIDENTIAL

This material is the property of the NYU School of Medicine and Langone Medical Center. Do not disclose or use except as authorized in writing by the study sponsor

- A detailed description of the event, incident, experience, or outcome;

CONFIDENTIAL

This material is the property of the NYU School of Medicine and Langone Medical Center. Do not disclose or use except as authorized in writing by the study sponsor

- An explanation of the basis for determining that the event, incident, experience, or outcome represents an UP;
- A description of any changes to the protocol or other corrective actions that have been taken or are proposed in response to the UP.

To satisfy the requirement for prompt reporting, UPs will be reported using the following timeline:

- UPs that are SAEs will be reported to the NIH within 48 hours of the investigator becoming aware of the event, and to the IRB within 5 working days.
- Any other UP involving risk to study participants or others will be reported to the NIH within 72 hours of the investigator becoming aware of the problem and to the IRB within 5 working days.
- All UPs should be reported to appropriate institutional officials (as required by an institution's written reporting procedures), the supporting agency head (or designee), and OHRP within two weeks of the IR's receipt of the report of the problem from the investigator.

8.4.4 Reporting of Pregnancy

The target study population (adults ≥ 65 years) for this research study does not include women who are of childbearing potential, pregnant or breastfeeding.

8.5 Reporting Procedures – Notifying the Study Sponsor

The study clinician will complete a SAE Form within the following timelines:

- In the unlikely event that serious and unanticipated and related adverse events or unanticipated problems involving risks to participants or others occur, they will be reported in writing within 72 hours to the IRB and the National Institutes of Health.
- Other SAEs regardless of relationship will be submitted to the NIH within 48 hours of site awareness.

All SAEs will be followed until satisfactory resolution or until the site investigator deems the event to be chronic or the adherence to be stable. Other supporting documentation of the event may be requested by the sponsor and should be provided as soon as possible.

As a follow-up to the initial report, within the following 48 hours of awareness of the event, the investigator shall provide further information, as applicable, on the unanticipated event or the unanticipated problem in the form of a written narrative. This should include a copy of the completed Unanticipated Problem form, and any other diagnostic information that will assist the understanding of the event. Significant new information on ongoing unanticipated adverse effects shall be provided promptly to the study sponsor.

8.6 Reporting Procedures – Participating Investigators

The Principal Investigators will inform fellow investigators and study personnel, via email, of all adverse events that occur during the conduct of this research project as they are reviewed.

8.7 Study Halting Rules

Administration of study will be halted when the DSMB deems appropriate. The DSMB will review AE listing reports and convene an ad hoc meeting by teleconference or in writing as soon as possible. The DSMB will provide recommendations for proceeding with the study to the NIH.

CONFIDENTIAL

This material is the property of the NYU School of Medicine and Langone Medical Center. Do not disclose or use except as authorized in writing by the study sponsor

Other risks that may warrant the halt of the study are indicated in Section 5.7.3, Premature Termination or Suspension of Study.

8.8 Safety Oversight

It is the responsibility of the Principal Investigator to oversee the safety of the study at his/her site. This safety monitoring will include careful assessment and appropriate reporting of adverse events as noted above, as well as the construction and implementation of a site data and safety-monitoring plan. Medical monitoring will include a regular assessment of the number and type of serious adverse events.

Safety oversight will be under the direction of a DSMB composed of individuals with the appropriate expertise, including 3 physicians (at least 1 cardiologist and 1 geriatrician) and 1 biostatistician. The DSMB will meet in-person once during Year 1 (first DSMB meeting) and will meet at least twice per year via teleconference to review study progress, data quality and participant safety. The DSMB will operate under the rules of an approved charter that will be written and reviewed at the organizational meeting of the DSMB. At this time, each data element that the DSMB needs to assess will be clearly defined. The DSMB will provide its input to NIH staff.

8.8.1 Events/Data to be Reviewed by DSMB

The DSMB will review the following:

Safety Monitoring Events.

- Listing of all Adverse Event (AE) by hospital and participants over time – expected or unexpected, and related or non-related to treatment
- Listing of all Serious Adverse Event (SAE) by hospital and participants over time - expected or unexpected, and related or non-related to treatment
- Listing of Unanticipated Problems (UP) by hospital and participants over time - expected or unexpected, and related or non-related to treatment
- Listings of all currently unresolved AEs
- Listings of all currently unresolved SAEs

Data Management.

- Percentage of participants accrued via an accrual report, by hospital and month of enrollment
- Percentage of participants at various stages of the study protocol (e.g., screening, enrollment, follow-up, completed)
- Percentage of missed visits, by treatment group
- Number of participants who completed follow-up visits to date, by treatment group
- Number of screening failures by treatment group over time
- Number of participants who terminated the study early by treatment group over time

8.8.2 Pre-Specified Stopping Rules

Recommendations for stopping of the trial due to evidence of benefit or harm will be based on statistical guidelines specified before the start of the trial and other internal and external factors considered relevant by the Committee members.

Circumstances that may warrant termination or suspension include, but are not limited to:

- Determination of unexpected, significant, or unacceptable risk to participants
 - Major risks include fall-related injury requiring medical care (inpatient hospitalization) that occurs during study-directed exercise, hospitalization for acute coronary syndrome, or hospitalization for unstable arrhythmia.

CONFIDENTIAL

This material is the property of the NYU School of Medicine and Langone Medical Center. Do not disclose or use except as authorized in writing by the study sponsor

- Demonstration of efficacy and engagement that would warrant stopping
- Insufficient compliance to protocol requirements
- Data that are not sufficiently complete and/or evaluable
- Determination of futility

Recommendations for stopping of the trial due to evidence of futility will not be based on pre-specified criteria, but rather will be based on a consensus that a combination of recruitment shortfall and/or other problems with adherence to the study protocol have created a situation in which the likelihood of successful assessment of the study aims is very low and not amenable to remediation through revision of the study protocol.

A decision to override the pre-specified stopping points must be based on a sound scientific analysis derived from internal or external data (e.g., ethical, statistical, practical, or financial) that provides a clear rationale for study continuation and must be unanimously approved by all DSMB voting members. After appropriate discussion, the Chairperson will summarize and encourage a consensus opinion.

8.8.3 Dissemination of Decision by DSMB

The Chairman of the DSMB will send a communication by email containing its recommendations to the Principal Investigator ([name]) within 14 days after each meeting. The Principal Investigator will then communicate the decision from the DSMB to the UMMHC and Yale Principal Investigator within 24 hours.

9 Clinical Monitoring

Clinical site monitoring is conducted to ensure that the rights and well-being of human subjects are protected, that the reported trial data are accurate, complete, and verifiable, and that the conduct of the trial is in compliance with the currently approved protocol/amendment(s), with GCP, and with applicable regulatory requirement(s).

- The contact Principal Investigator (PI), [name], will be responsible for ensuring all participants' safety through targeted random review on a monthly basis throughout the study period.
- Independent audits will be conducted by the DSMB to ensure monitoring practices are performed consistently across all participating sites.

10 Statistical Considerations

10.1 Statistical and Analytical Plans (SAP)

The statistical plan is delineated for the primary, secondary, and exploratory outcomes below.

10.2 Statistical Hypotheses

Primary Endpoints

Efficacy: 6 minute walk distance (6MWD)

Hypothesis: Degree of improvement in 6MWD will be greater in participants assigned to mHealth-CR than in those assigned to usual care.

Engagement: Mobile health (mHealth) use

CONFIDENTIAL

This material is the property of the NYU School of Medicine and Langone Medical Center. Do not disclose or use except as authorized in writing by the study sponsor

Hypotheses: (1) Among participants offered mHealth-CR, there will be distinct trajectories of engagement (e.g., sustained engagement, disengagement, reengagement, deteriorating engagement); and (2) there will be significant differences in participant characteristics among these groups.

Secondary Endpoints

1. Goal attainment (measured by Goal Attainment Scaling)
2. Health status (measured by SF-12 and SAQ)
3. Activities of daily living (ADLs)
4. Hospital readmission
5. Death

Hypotheses: Goal attainment scaling, health status, and ADLs will improve in participants who are offered mHealth-CR compared with usual care. Hospital readmission and death will be lower in participants who are offered mHealth-CR compared with usual care.

10.3 Analysis Datasets

All randomized participants will be analyzed according to the treatment group to which they were randomized, regardless of subsequent crossover. The intent-to-treat (ITT) population will include all subjects who receive a randomized treatment assignment, except for those with a documented violation of trial eligibility criteria.

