- *Hospital readmission* is defined as an overnight stay (including observation) in any hospital within 3 months of discharge. Readmissions in older adults with IHD are common, costly, and disruptive; multiple entities within the U.S. healthcare system emphasize reducing potentially preventable readmissions.⁷² Since these data are obtainable via the electronic health record (EHR), we will also ascertain readmission events at 6 months and 1 year.
- *Death* is defined by death from any cause within 3 months of enrollment. Given our sample size, we do not expect to detect a significant difference in mortality rates, but a descriptive analysis may place other endpoints in context. In addition, absolute mortality rates can assist with planning of subsequent studies. Similar to readmission, we will also ascertain death at 6 months and 1 year through the EHR.

Safety Endpoint. The safety endpoint will be assessed at the 3-month ambulatory visit and includes (1) fall-related injury (operationalized as any fall requiring acute medical care); (2) hospitalization for acute coronary syndrome; and (3) hospitalization for unstable arrhythmia. Separately, among intervention participants, study staff will monitor potential exercise-related adverse events on an ongoing basis. Points of contact will include weekly phone calls with the exercise therapist as well as electronic communication via the mHealth app which is checked daily. All adverse events will be reported directly to the Principal Investigator and to the DSMB. In order to reduce the likelihood of these events, participants will complete the baseline 6MWT in-hospital; if any adverse event occurs during 6MWT (drop in SBP ≥ 15 mmHg, chest pain, ventricular arrhythmia), participants will be removed (not randomized). Other exclusion criteria (severe osteoarthritis, recent joint replacement,

CONFIDENTIAL

This material is the property of the NYU School of Medicine and Langone Medical Center. Do not disclose or use except as authorized in writing by the study sponsor

moderate or severe cognitive impairment) are also intended to minimize risk. Prior studies of home-based CR have reported that adverse events are uncommon.^{73,74}

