5.1 Inclusion Criteria

In order to be eligible to participate in this study, an individual must meet all of the following criteria:

1. Age ≥ 65 .
2. Currently hospitalized for AMI, PCI, or CABG **or**
Hospitalized for AMI, PCI or CABG within prior 4 weeks.
3. Capable of self-consent.
4. Understand and are able to perform study procedures (i.e. 6-minute walk test, use mHealth in English or Spanish).

Given logistical considerations, we expect that most participants with AMI and/or PCI will be recruited from the inpatient setting, with the baseline assessment taking place before discharge. However, given recent trends in AMI and PCI care (shorter hospital stays, including same-day discharge after PCI), we may not be able to capture all eligible participants at the time of hospitalization. In this case, the baseline study visit will take place at the first ambulatory cardiology visit (provided this occurs within 4 weeks of hospitalization). Since patients undergoing CABG have exposure to much greater physiologic stress as they recover from surgery, our expectation is that they will not be enrolled in the hospital (given inability to participate in mHealth-CR immediately after discharge), but instead will be enrolled at the first ambulatory visit (provided within 4 weeks of discharge). For patients with AMI or PCI, they can be enrolled either in the hospital or the first ambulatory visit (provided within 4 weeks of discharge).

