5.2 Exclusion Criteria

An individual who meets any of the following criteria will be excluded from participation in this study:

1. Non-ambulatory.
2. Moderate or severe cognitive impairment.

CONFIDENTIAL

This material is the property of the NYU School of Medicine and Langone Medical Center. Do not disclose or use except as authorized in writing by the study sponsor

3. Unable/unwilling to consent.
4. PCI-related groin hematoma that precludes brisk walking.
5. Incarcerated.
6. Unable to use mHealth software in English or Spanish.
7. Severe osteoarthritis, or joint replacement within last 3 months.

Parkinson's disease or other progressive movement disorder.

8. Regular use of walker for ambulation.
9. Projected life expectancy <3 months.
10. Clinical judgment concerning other safety or nonadherence issues.
11. Participants admitted from long-term care facility.
12. Currently listed for heart transplant.
13. Left ventricular assist device recipient.
14. Completion of ambulatory cardiac rehabilitation program within prior 3 months.

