10.4.6 Baseline Descriptive Statistics

An enrollment summary will be provided giving the total number of enrolled patients by participating hospital, with both monthly and cumulative totals provided on an ongoing basis. Baseline demographic and clinical characteristics will be tabulated by hospital for the ITT population.

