with our expected sample of 320 patients, using two-sided, 0.05-level tests; we will not implement multiple comparisons correction for these secondary outcomes. Baseline event rates and standard deviations are estimated from the literature.¹¹⁵⁻¹¹⁸ For example, we have 90% power to detect a difference between groups of 5 units in the SF-12 score.

All comparisons between the randomized groups in this trial will be performed according to the principle of "intention-to-treat"; that is, participants will be analyzed according to the treatment group to which they were randomized, regardless of subsequent crossover. The intent-to-treat (ITT) population will include all subjects who receive a randomized treatment assignment, except for those with a documented violation of trial eligibility criteria.

The table below shows clinically meaningful effect sizes for secondary efficacy outcomes, and gives the power to detect these effect sizes with our expected sample of 320 patients, using two-sided, 0.05-level tests; we will not implement multiple comparisons correction for these secondary outcomes.

Outcome	Endpoint definition	Effect size	Estimated s.d.	Power
Goal attainment scaling	GAS score	5	15	73%
Health status	SF-12	5	12	90%
Health status	Residual angina on SAQ	15-20%	n/a	67-93%
ADLs	Standardized ADL score	15-20%	1	64-87%
Hospital readmission	Admission by 3 months	15%	n/a	91%
Death	Death by 3 months	10%	n/a	82%

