14.3 Protocol Deviations

A protocol deviation is any noncompliance with the clinical trial protocol or GCP requirements. The noncompliance may be either on the part of the participant, the investigator, or the study site staff. As a result of deviations, corrective actions are to be developed by the site and implemented promptly.

These practices are consistent with ICH E6:

- 4.5 Compliance with Protocol, sections 4.5.1, 4.5.2, and 4.5.3
- 5.1 Quality Assurance and Quality Control, section 5.1.1
- 5.20 Noncompliance, sections 5.20.1, and 5.20.2.

It is the responsibility of the site PI/study staff to use continuous vigilance to identify and report deviations within 5 working days of identification of the protocol deviation, or within 5 working days of the scheduled protocol-required activity.

All protocol deviations must be addressed in study source documents, reported to NIA Program Official.

Protocol deviations must be reported to the local IRB per their guidelines. The site PI/study staff is responsible for knowing and adhering to their IRB requirements. Further details about the handling of protocol deviations will be included in the MOP.

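### The only analysis population is labelled ITT but removes randomised participants with a documented eligibility violation, with no timing or blinding rule and no all-randomised analysis

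*Combined protocol and SAP*

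**What the plan says.** Section 10.3 opens with a general rule: "All randomized participants will be analyzed according to the treatment group to which they were randomized, regardless of subsequent crossover". The next sentence defines the ITT population as "all subjects who receive a randomized treatment assignment, except for those with a documented violation of trial eligibility criteria". Section 10.5 says that all between-arm comparisons follow intention-to-treat, then repeats the exception: "except for those with a documented violation of trial eligibility criteria". No all-randomised, per-protocol or safety set is defined, and no sensitivity analysis brings the removed participants back.

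Related provisions:

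- **Masking.** Section 10.6.3 blinds only the 6MWT assessor. Section 7.2.4 adds a blinded GAS assessor at the 3-month visit.
- **Late recognition.** Section 5.7.1 lets an investigator end participation when an exclusion criterion newly develops or comes to light after entry.
- **Deviations.** Section 14.3 requires deviations to be reported within 5 working days and adds: "Further details about the handling of protocol deviations will be included in the MOP". The MOP is not among the documents.
- **Reporting.** Section 10.4.6 says: "Baseline demographic and clinical characteristics will be tabulated by hospital for the ITT population". Section 10.4.1 plans a check of balance by intervention group. Section 10.6.1 has population denominators shown in column headers.

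**The concern.** Randomisation protects the comparison only if everyone randomised stays in it, or if removals depend solely on facts fixed before randomisation and judged without knowledge of arm or outcome. The plan secures neither condition. A violation of eligibility criteria ordinarily means that the person was ineligible at entry, but the text does not say so. It also sets no cut-off date, names no adjudicator and requires no blinding.

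The opening sentence of 10.3 can be read as fixing only the arm in which people are analysed. On that reading it does not contradict the exception, but there is still no all-randomised analysis. If it is taken literally, the two sentences conflict. Either way, the definition that governs the analysis is stated twice and removes randomised people.

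If violations were documented more often in the intervention arm, and those removed would have had a worse change in 6MWD, the primary comparison would lean towards mHealth-CR. For readmission and death, which section 4.2.2 allows to be ascertained from the health record, the clause could discard outcomes that were actually observed.

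**Working it through.** **Inputs from section 10.5.** 400 randomised 3:1 (300 and 100); 20% dropout, leaving 240 and 80 evaluable; SD of change 60 m; two-sided 0.05. Section 10.4.2 plans a t-test allowing unequal variances.

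**The plan's own figure.** SE = 60 × √(1/240 + 1/80) = 7.75 m. For 25 m, 25/7.75 = 3.23. Power is 0.898 by the normal approximation and 0.893 by the noncentral t with Welch degrees of freedom (about 135). For 22 m it is 0.811 and 0.805. Both agree with the stated 90% and 80%, and 320/0.8 = 400. No planned figure is in dispute.

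**Assumptions.** The documents give no violation rate. Suppose there is no true treatment effect. In each arm a fraction f of evaluable participants are violators, and their mean change is g metres worse than that of the rest. Shares d_i (intervention) and d_c (usual care) of the violators are detected and removed.

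**Formula.** After removal, the violator share left in an arm is f(1 − d)/(1 − f·d). The shift in the intervention-minus-control difference is therefore

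bias = −g·f(1 − d_i)/(1 − f·d_i) + g·f(1 − d_c)/(1 − f·d_c)

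Type I error comes from the noncentral t with n = 240(1 − f·d_i) and 80(1 − f·d_c).

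**Worked case.** f = 5%, g = 60 m, d_i = 0.8, d_c = 0.2:

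- intervention: −60 × 0.05 × 0.2/0.96 = −0.625 m
- usual care: −60 × 0.05 × 0.8/0.99 = −2.424 m
- bias = −0.625 + 2.424 = 1.80 m
- n = 230.4 and 79.2; SE = 7.82 m; type I error = 0.056

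**Range.**

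| Detection (intervention / usual care) | f | g (m) | Bias (m) | Type I error |
|---|---|---|---|---|
| 100% / 0% | 1-2% | 15-60 | 0.15-1.2 | 0.050-0.053 |
| 100% / 0% | 5% | 30 | 1.5 | 0.054 |
| 100% / 0% | 5% | 60 | 3.0 | 0.067 |
| 100% / 0% | 10% | 30 | 3.0 | 0.067 |
| 100% / 0% | 10% | 60 | 6.0 | 0.118 |
| 80% / 20% | 5% | 60 | 1.8 | 0.056 |
| 80% / 20% | 10% | 60 | 3.6 | 0.074 |
| 80% / 50% | 10% | 60 | 1.9 | 0.056 |
| Equal (50% / 50%) | any | any | 0 | 0.050 |

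**Violators without a 3-month walk.** Only violators who have a 3-month 6MWD can be affected by the clause. Take f = 10% of those randomised, g = 60 m and intervention-only detection, and let a share r of violators have the measurement (relative to the rest). The evaluable violator share becomes f·r/(f·r + 1 − f). For r = 50% this is 0.05/0.95 = 5.3%, so the bias is 60 × 0.053 = 3.2 m (type I error 0.068). For r = 25% it is 1.6 m (0.055), and for r = 0 it is 0 m (0.050).

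**The case against.** Five points on the other side deserve weight.

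1. **Screening comes before randomisation.** Records are screened and reviewed by an investigator (5.4, 7.2.1), criteria are verified at baseline (7.2.2), and the walk test precedes randomisation (7.1.1). High violation rates are therefore less likely, and no document supports 5-10%. This stands, and it is why the low-rate rows matter most.

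2. **Late-recognised violators may have no 6MWD anyway.** Under 5.7.1 they may be terminated, and under 5.7.2 they would not return. Their walk distance is then missing under any definition. This stands in part: termination is at the investigator's discretion, and readmission and death do not need a visit.

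3. **Removals are not invisible.** A reader might infer that nobody could tell how many people were dropped. That goes too far. With the denominators promised in 10.6.1, the number removed can be derived from the number randomised. What is missing is the reasons by arm and any planned comparison that includes the excluded participants' outcomes.

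4. **Unequal detection is not shown.** A reader might infer that non-users of the app would be reclassified as ineligible, because "Unable to use mHealth software in English or Spanish" is an exclusion and only the intervention arm receives the software. That needs the criterion to mean technical ability. Read as a language requirement, it is visible in both arms. The plan also has another place for non-use, the engagement score, and section 10.4.4 keeps intervention participants stopped for adverse events under intention-to-treat. Nothing says that low use becomes an eligibility violation.

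5. **The MOP may settle the matter.** It may add rules on deviations. Who is analysed nevertheless belongs in the analysis plan, and the definition given there is explicit.

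**Conclusion.** The definition should be corrected. The sole population is not intention-to-treat as labelled, it sits badly with the plan's own opening rule, and the conditions that would make the exclusion harmless are not stated. This rests on the text alone.

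The numerical consequence is conditional. It is negligible at 1-2% violators, about 1.8 m (type I error 0.056) at 5% with 80% against 20% detection and a 60 m worse change, and nil when detection is equal. The 3.0-6.0 m and 0.067-0.118 results need 5-10% violators with follow-up, a gap of a full SD, and detection only in the intervention arm. A reader might take the top of that range as the trial's expected error rate, or conclude that the trial is biased towards mHealth-CR. The documents support neither: they give no violation rate and no evidence of unequal detection. The calculations assume equal violator rates and equal gaps in the two arms and apply to the t-test on change scores.

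**What to change.** In 10.3 and 10.5 delete "except for those with a documented violation of trial eligibility criteria" and define ITT as all randomised participants, analysed in the arm assigned. If an eligibility-based exclusion is wanted, keep it as a sensitivity analysis only. Limit it to facts that pre-date randomisation, have it judged blind to arm and outcome, and report counts and reasons by arm.

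The cost is one clause in two sections and a sentence describing the sensitivity set. No visit or test is added. The planned 400 randomised and 320 evaluable are unchanged, and so is power (0.893 at 25 m and 0.805 at 22 m by the Welch calculation). The downside is slightly more heterogeneity. Sections 5.7.2 and 7.2.5 differ on the final visit after withdrawal; that is a separate matter and not part of this change.
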